#### 7.3.11. Incidence of incorrect phonemes

[figure not shown]

[figure not shown]
[figure not shown]
[figure not shown]

[figure not shown]
[figure not shown]
[figure not shown]
[figure not shown]
- *Computation of the Endpoint*

In each word recognition list, there are 150 phonemes represented across the 50 words with exactly 3 phonemes per word. The 150 phonemes are not uniformly or uniquely represented, but distributed with frequencies empirically approximating real-world use (Causey et al., 1984). For each unique phoneme, the percentage not recognized correctly will be computed by subject, visit, and ear.

- *Analysis of the Endpoint*

Heat maps will be produced by visit and treatment group for treated ears to graphically display the incidence of incorrect phonemes for subjects in the FAS. The x-axis will include a column for each unique phoneme and the y-axis will include a row for each subject. The shading for each cell of the map will represent the percentage of phonemes not recognized correctly.

Shading Color	Percentage Incorrect
	>=90%
	80 to <90%
	70 to <80%
	60 to <70%
	50 to <60%
	40 to <50%
	30 to <40%
	20 to <30%
	10 to <32%
	<=10%

Post hoc analyses may be performed on select unique phonemes of interest, based on the final results of the heat map described above. The post hoc analyses may include heat maps by visit for treated ears also taking into account the location of the phoneme within the word (phoneme/location) for subjects in the FAS. Post hoc treatment group comparisons may also be performed.

- *Sensitivity Analyses of the Endpoint*

None.

#### 7.4. Words-In-Noise

WIN is measured using the incidence of correctly recognized words in the presence of background noise using multitalker babble (Wilson et al., 2003). Materials are recorded at 7 signal-to-noise ratios (0, 4, 8, 12, 16, 20, 24 dB) that are presented in a descending manner. The test consists of 2 lists of 35 recorded words (70 total) for each ear and the number of and percentage of correctly recognized words at each signal-to-noise ratio will be recorded separately by ear. The overall WIN score will be recorded as the percentage of correctly recognized words across all signal-to-noise ratios by visit and ear. If all 70 words are not assessed in each ear, the WIN test score will not be calculated.

The WIN test will be performed at Screening, Day 15, 60, 90, 150, and 210 visits. Testing will be performed at 80 dB sound pressure level (SPL) and word lists will be rotated at each visit. Additional details can be found in the Audiology Manual of Procedures.

Baseline scores for analysis will be computed from the Screening visit. There will be no imputation for missing scores.

##### 7.4.1. Number of recognized words

- *Computation of the Endpoint*

At each visit and by ear (left, right), the number of words classified as correctly recognized at each signal-to-noise ratio will be recorded. The overall WIN score will also be computed as the number of words correctly recognized across all signal-to-noise ratios. Left and right ears will be mapped to treated and untreated for analysis, as described in Section 3.

In subjects in the FAS with hearing loss in both ears per the Targeted Hearing Loss History CRF page, the ratio of the number of recognized words for treated ear versus untreated ear will be computed.

- *Analysis of the Endpoint*

The number of recognized words at each signal-to-noise ratio and overall will be summarized descriptively for treated and untreated ears separately by visit and treatment group for subjects in the FAS.

Treatment group comparisons for the number of recognized words overall will be performed using the approach described in Section 7.4.4 for subjects in the FAS. The covariance structure (UN or AR(1)) that provides the best model fit for the relative percent change from baseline in percentage of recognized words, as described in Section 7.4.4, will be implemented with a repeated statement in SAS. Treatment group comparisons will not be performed for each signal-to-noise ratio.

The ratio of the number of recognized words for treated ears versus untreated ears will be summarized descriptively by visit and treatment group for all subjects in the FAS, subjects in the FAS with bilateral hearing loss, and subjects in the FAS without bilateral hearing loss.

- *Sensitivity Analyses of the Endpoint*

The analyses will be repeated for subjects in the PPAS.

If there are any dosing administrations errors such that a not qualified ear is treated, the descriptive summaries by treated and untreated ears will be repeated for subjects in the FAS including all treated and untreated ear data.

#### 7.4.2. Percentage of recognized words

- *Computation of the Endpoint*

Using the number of recognized words in Section 7.4.1, the percentage of recognized words will be computed for each signal-to-noise ratio by visit as the number of recognized words divided by 10 and multiplied by 100, separately for each ear. The percentage of recognized words overall by visit will be computed as the number of recognized words divided by 70 and multiplied by 100, separately for each ear.

- *Analysis of the Endpoint*

The percentage of recognized words at each signal-to-noise ratio and overall will be summarized descriptively for treated and untreated ears using the approach described in Section 7.4.1 for subjects in the FAS.

Line graphs (with standard error bars) will be created for the observed percentage of recognized words at each signal-to-noise ratio for treated ears by visit and treatment group for subjects in the FAS. The signal-to-noise ratio will be plotted on the x-axis and the

percentage of recognized words will be plotted on the y-axis. There will be separate lines for each treatment group and possibly separate plots for each visit. All treatment groups and visits may be included in a single plot, if the lines are not too crowded.

Treatment group comparisons for the percentage of recognized words overall will be performed using the approach described in Section 7.4.4 for subjects in the FAS. The covariance structure (UN or AR(1)) that provides the best model fit for the relative percent change from baseline in percentage of recognized words, as described in Section 7.4.4, will be implemented with a repeated statement in SAS. Treatment group comparisons will not be performed for each signal-to-noise ratio.

- *Sensitivity Analyses of the Endpoint*

With the exception of the line graphs, the analyses will be repeated for subjects in the PPAS.

If there are any dosing administrations errors such that a not qualified ear is treated, the descriptive summaries by treated and untreated ears will be repeated for subjects in the FAS including all treated and untreated ear data.

#### 7.4.3. Absolute percent change from baseline in percentage of recognized words

- *Computation of the Endpoint*

The absolute percent change from baseline to each post-baseline visit in percentage of recognized words at each signal-to-noise ratio will be computed as  $100 * [(w/10) - (b/10)]$  where “w” is the frequency of words recognized at the post-baseline visit and “b” is the frequency of words recognized at baseline. The absolute percent change from baseline to each post-baseline visit in percentage of recognized words overall will be computed using the same algorithm, but with 70 words in the denominator instead of 10.

- *Analysis of the Endpoint*

The absolute percent change from baseline in percentage of recognized words at each signal-to-noise ratio and overall will be summarized descriptively for treated and untreated ears using the approach described in Section 7.4.1 for subjects in the FAS.

Line graphs (with standard error bars) will be created for the adjusted (least squares) mean absolute percent change from baseline in percentage of recognized words overall for treated ears by post-baseline visit and treatment group for subjects in the FAS. Post-baseline visit will be plotted on the x-axis and the adjusted (least squares) mean absolute percent change from baseline in percentage of recognized words overall for treated ears will be plotted on the y-axis. Each treatment group will be presented as a separate line in the plot. The line graphs will be repeated for the observed mean absolute percent change from baseline in percentage of recognized words overall for treated ears.

Treatment group comparisons for the absolute percent change from baseline in percentage of recognized words overall will be performed using the approach described in Section 7.4.4

for subjects in the FAS. The covariance structure (UN or AR(1)) that provides the best model fit for the relative percent change from baseline in percentage of recognized words overall, as described in Section 7.4.4, will be implemented with a repeated statement in SAS. Treatment group comparisons will not be performed for each signal-to-noise ratio.

- *Sensitivity Analyses of the Endpoint*

With the exception of the line graphs, the analyses will be repeated for subjects in the PPAS.

If there are any dosing administrations errors such that a not qualified ear is treated, the descriptive summaries by treated and untreated ears will be repeated for subjects in the FAS including all treated and untreated ear data.

#### 7.4.4. Relative percent change from baseline in percentage of recognized words

- *Computation of the Endpoint*

The relative percent change from baseline to each post-baseline visit in percentage of recognized words at each signal-to-noise ratio will be computed as  $100 \cdot [(w-b)/b]$  where “w” is the frequency of words recognized at the post-baseline visit and “b” is the frequency of words recognized at baseline. The relative percent change from baseline to each post-baseline visit in percentage of recognized words overall will be computed using the same algorithm, but with “w” and “b” scores for all 70 words at each visit.

- *Analysis of the Endpoint*

The relative percent change from baseline in percentage of recognized words at each signal-to-noise ratio and overall will be summarized descriptively for treated and untreated ears using the approach described in Section 7.4.1 for subjects in the FAS.

Line graphs (with standard error bars) for the adjusted (least squares) means and observed means will be created using the approach described in Section 7.4.3 for subjects in the FAS.

In treated ears only for subjects in the FAS, treatment group comparisons for the relative percent change from baseline in percentage of recognized words overall will be analyzed using a mixed-effect, repeated measures model using fixed covariates for treatment group, WR score at baseline (<50% versus ≥50%), etiology of hearing loss (SSNHL versus NIHL), visit, and interaction between visit and treatment group. As described in Section 7.3.4, separate models will be fit specifying UN and AR(1) covariance structures (implemented with a repeated statement in SAS). The covariance structure providing the lowest corrected AICc and BIC values from the model will be implemented for the relative percent change from baseline and all other WIN endpoints. The treatment group differences analyzed will be between each FX-322 group (including the pooled FX-322 group) versus placebo, and comparisons between the individual FX-322 groups (excluding the pooled FX-322 group). Comparisons will be made by visit (e.g., estimated LS Mean differences by visit) and overall (e.g., Type III Sums of Squares). Treatment group comparisons will not be performed for each signal-to-noise ratio.

- *Sensitivity Analyses of the Endpoint*

With the exception of the line graphs, the analyses will be repeated for subjects in the PPAS.

If there are any dosing administrations errors such that a not qualified ear is treated, the descriptive summaries by treated and untreated ears will be repeated for subjects in the FAS including all treated and untreated ear data.

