### **8.4.2 Inclusion Criteria**

To be eligible for study entry subjects must satisfy all of the following criteria:

1. Subject has read and voluntarily signed the Informed Consent Form (ICF) after all questions have been answered and prior to any study-mandated procedure.
2. Adult aged 18-65 years inclusive.
3. Established diagnosis of stable sensorineural hearing loss by standard audiometric measures for  $\geq 6$  months prior to the Screening visit (no changes in air conduction greater than 10 dB at a single frequency or greater than 5dB at two contiguous frequencies from the prior audiogram to the Screening audiogram in the study ear).
4. Documented medical history consistent with hearing loss being caused by noise exposure or sudden sensorineural hearing loss (documented audiogram at least 6 months prior to screening required).
5. A pure tone average of 26-70 dB at 500Hz, 1000Hz, 2000Hz, and 4000Hz in the ear to be injected.
6. Subjects with a 15% - 85% correct score on Word Recognition test (8 – 42 words correct out of 50) at Screening in the study ear.
7. Ability to communicate well with the Investigator and is willing to comply with and complete all the study procedures.
8. Female subjects must be of non-childbearing potential or will need to utilize two methods of highly effective contraception during the study participation (e.g. hormonal contraception or an intrauterine device and condoms) or remain abstinent. Male subjects

should use condoms with spermicide during the course of the study or remain abstinent. Subjects should not donate sperm or ova during the study period.

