#### **14.1.5 Efficacy Exploration**

Efficacy endpoints will be summarized descriptively at each study timepoint including baseline. Calculations will include the observed data at each timepoint, and if relevant, the change from baseline. For continuous endpoints means, medians, standard deviations, minimums and maximum will be provided. For categorical endpoints the number and percent of subjects within each category will be calculated. Tabulations for selected endpoints will be presented by subgroups such as age, study site, duration of hearing loss, smoking status, and stratification factors used at randomization. Details will be provided in the SAP. For descriptive analyses, subjects with missing data will be excluded for a particular calculation.

For questionnaires, the analysis will follow the instructions for scoring and handling of missing data appropriate for the particular instrument.

Inferential statistical methods examining continuous endpoints will be examined via a Mixed Model for Repeated Measures (MMRM). Analyses will include pairwise contrasts and dose response. Inferential analyses for categorical endpoints will be analysed using univariate methods and/or Generalized Linear Mixed Models (GLMM). When appropriate, models will include adjustments for baseline as well as the stratification factors used at randomization. Departures of these models from the statistical assumptions will be assessed and alternative approaches maybe employed. Additionally, univariate models such as Analysis of Covariance and/or count models examining single timepoints of interest may also be examined. General methods for handling missing data for inferential analyses are described below (Section 14.2).

The inferential analyses will not be adjusted for multiple endpoints; however, for a given endpoint, adjusted p-values for pairwise comparisons to a control will be provided where

relevant along with the unadjusted p-values. Unadjusted 95% confidence intervals will also be provided. In some circumstances, adjusted confidence intervals may be calculated.

Efficacy endpoints will be analysed using the FAS. Further details regarding the exploratory analysis of efficacy will be outlined in the SAP.

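### SAP 7.4.4 plans relative percent change in Words-In-Noise at each signal-to-noise ratio, with no rule for a baseline of 0 out of 10 words

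*SAP*

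**What the plan says.** SAP 7.4 describes the test: "The test consists of 2 lists of 35 recorded words (70 total) for each ear", spread over seven SNRs from 24 dB down to 0 dB. In SAP 7.4.2 the percentage at each SNR is the "number of recognized words divided by 10 and multiplied by 100", so each level rests on 10 words.

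SAP 7.4.4 defines relative change as 100 × (w − b)/b, where b "is the frequency of words recognized at baseline". It applies this both at each SNR and to the 70-word total, and states that the "relative percent change from baseline in percentage of recognized words at each signal-to-noise ratio and overall will be summarized descriptively". The summaries are by visit and group, for treated and untreated ears, and are repeated in the per-protocol set. The same section makes no treatment comparison at individual SNRs.

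Three further statements bear on b = 0:

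- SAP 7.4: "There will be no imputation for missing scores".
- Protocol 14.1.5: "For descriptive analyses, subjects with missing data will be excluded for a particular calculation".
- Protocol 8.4.2 requires a "15% - 85% correct score on Word Recognition test" in the study ear. That is a test in quiet. No criterion concerns WIN.

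SAP 3, 7.1.6, 7.4 and 7.4.4 contain no rule for a baseline of zero.

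**The concern.** A ratio to baseline needs a baseline that stays away from zero. For word recognition in quiet (SAP 7.3.4) eligibility secures this in the study ear, because the criterion means at least 8 of 50 words. Nothing does so for WIN, least of all for 10 words at 0 or 4 dB.

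Two things then go wrong in the low-SNR rows. First, ears with b = 0 have no value and leave the row, and the loss is one-sided because such an ear can only stay at zero or improve. Second, the ears that remain were selected for having scored at least one word. Their follow-up scores regress towards their true level, while a baseline of 1 word turns every extra word into +100%. A reader of these rows could miss a real gain or see a deterioration that did not happen.

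**Working it through.** **1. Words per SNR.** 2 lists × 35 words / 7 SNRs = 10, and 7 × 10 = 70. Both agree with the denominators in SAP 7.4.2.

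**2. The formula at b = 0.** For b = 0 and w = 3, relative change is 100 × 3/0, which is undefined. The absolute change in SAP 7.4.3 is 100 × (3/10 − 0/10) = +30 points.

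**3. How often b = 0.** The documents give no WIN recognition rates, so the probability p of recognizing a word is an assumption. With 10 independent words, P(b = 0) = (1 − p)^10.

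| Assumed p | P(b = 0) | Expected out of 24 |
|---|---|---|
| 0.01 | 0.904 | 21.7 |
| 0.05 | 0.599 | 14.4 |
| 0.10 | 0.349 | 8.4 |
| 0.20 | 0.107 | 2.6 |
| 0.30 | 0.028 | 0.7 |

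To link p to the SNR, assume p = 1/(1 + exp(−(SNR − T)/s)), with midpoint T and scale s in dB. Each cell gives P(b = 0) for s = 4 and then for s = 2.5.

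| T | 0 dB | 4 dB |
|---|---|---|
| 10 | 0.45, 0.83 | 0.13, 0.42 |
| 14 | 0.74, 0.96 | 0.45, 0.83 |
| 18 | 0.90, 0.99 | 0.74, 0.96 |

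The ranges are 0.45–0.99 at 0 dB and 0.13–0.96 at 4 dB. At T = 14, between 24 × (1 − 0.96) ≈ 1 and 24 × (1 − 0.74) ≈ 6 subjects per group would remain at 0 dB.

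**4. Artefact with no true change.** Among retained ears the mean baseline is 10p/(1 − (1 − p)^10), and the expected follow-up count is 10p. Mean relative change is 100 × (10p × E[1/b given b ≥ 1] − 1).

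- p = 0.05: mean baseline 0.5/0.401 = 1.25 words, so the absolute change is 10 × (0.5 − 1.25) ≈ −7.5 points. Relative change is 100 × (0.5 × 0.888 − 1) ≈ −55.6%.
- p = 0.10: mean baseline 1/0.651 = 1.54 words, absolute change −5.4 points. Relative change is 100 × (1 × 0.778 − 1) ≈ −22.2%.
- p = 0.20: absolute change −2.4 points. Relative change is 100 × (2 × 0.577 − 1) ≈ +15.4%.

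Selection pulls the absolute mean of retained ears down in all three cases. The relative mean changes sign at p = 0.20, because small values of b in the denominator inflate the gains. The true change is zero throughout.

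**5. Artefact with a true gain.** If p rises from 0.10 to 0.20, the mean gain is +20.0 points in excluded ears, +4.6 in retained ears and +10.0 in all (0.349 × 20.0 + 0.651 × 4.6 ≈ 10.0).

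**6. Constructed example.** Of 24 ears, 10 go from 0 to 3 words and 14 stay at 4. Mean absolute change is (10 × 30 + 14 × 0)/24 = +12.5 points on n = 24. Mean relative change is 0.0% on n = 14, so the whole gain is lost.

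**7. The 70-word score.** Even with p = 0.10 at every SNR, P(b = 0 of 70) = 0.90^70 ≈ 0.06%. The overall relative change is practically free of the problem.

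**The case against.** The case for leaving the plan alone is that little depends on these rows, and most of it stands. The same ears remain in the per-SNR counts (SAP 7.4.1), percentages (7.4.2) and absolute change (7.4.3). Unless all 70 baseline words were missed, they also remain in the overall analyses. Ears with b from 1 to 9 can improve too and are kept. There is no single primary endpoint (SAP 7.2) and all p-values are descriptive (SAP 7.1.4).

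A reader might infer more than the documents support:

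- **That the retained subset is biased between arms.** WIN baseline comes from Screening (SAP 7.4), and randomization follows on Day 1 (Protocol 10.1.2). Selection on b ≥ 1 precedes allocation, so arms differ in this respect only by chance.
- **That ears disappear unseen.** SAP 3 requires the number of subjects, median, minimum and maximum for continuous variables. The smaller n would show, though unexplained, and the median tempers extreme percentages.
- **That b = 0 is the usual result at 0 and 4 dB.** The documents do not say so. At 4 dB the assumed model gives anything from 0.13 to 0.96.
- **That any rise from zero is clear improvement.** The critical-difference charts in SAP 14.1 and 14.2, supplied for word recognition in quiet, give 0–20% for a score of 0 on 10 words. By that standard 1 or 2 words is within chance, and 3 or more is not.

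None of this supplies a value at b = 0 or removes the distortion among retained ears.

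**Conclusion.** The point holds for the per-SNR relative-change rows of SAP 7.4.4 and no further. At hard SNRs the stated formula has no value for ears at the floor, and it misdescribes the ears that remain. The exclusion is inferred, not written: it follows from division by zero, the absence of imputation and Protocol 14.1.5.

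The size cannot be fixed from the documents. It rests on an assumed recognition probability, independent words and, for the artefact, a common p across ears. Real variation between ears would change the figures. The direction of the loss, with only non-worsening ears excluded, needs none of these assumptions. Because the rows are descriptive and a sound companion measure is already planned, this is a desirable correction and not an essential one.

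**What to change.** In SAP 7.4.4, restrict relative percent change to the overall 70-word score. By SNR, report only the absolute change already defined in SAP 7.4.3, which has a value at b = 0. The cost is the removal of one set of descriptive rows, with no new programming and no effect on the treatment comparisons.

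If the per-SNR rows are kept, state that relative change is not calculated when b = 0, and report the number of ears excluded for that reason by group, SNR and visit.

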where “pc” is the percentile of interest, “l” is the initial dB presentation level (fixed at 24), “d” is the attenuation dB step size (fixed at 4), “c” is the number of words per decrement (fixed at 10), and “w” is the frequency of words recognized overall at each visit.

- *Analysis of the Endpoint*

Spearman-Kärber estimates (25th, 50th (median) and 75th percentiles) will be summarized descriptively for treated ears by visit and treatment group for subjects in the FAS.

For each post-baseline visit, scatter plots of the median Spearman-Kärber estimates at baseline versus the post-baseline visit will be produced by treatment group for subjects in the FAS.

In treated ears only for subjects in the FAS, treatment group comparisons for the median Spearman-Kärber estimate will be analyzed using a mixed-effect, repeated measures model using fixed covariates for treatment group, WR score at baseline (<50% versus ≥50%), etiology of hearing loss (SSNHL versus NIHL), visit, and interaction between visit and treatment group. The covariance structure (UN or AR(1)) that provides the best model fit for the relative percent change from baseline in percentage of recognized words overall, as described in Section 7.4.4, will be implemented with a repeated statement in SAS. The treatment group differences analyzed will be between each FX-322 group (including the pooled FX-322 group) versus placebo, and comparisons between the individual FX-322 groups (excluding the pooled FX-322 group). Comparisons will be made by visit (e.g., estimated LS Mean differences by visit) and overall (e.g., Type III Sums of Squares).

- *Sensitivity Analyses of the Endpoint*

The analyses will be repeated for subjects in the PPAS.

